- Body Mass Index 18.5 – 50 kg/m², based on self-reported height and weight
- Shops for groceries
- Conducts some of the food shopping and food preparation for their household
- Be willing to do food shopping for the study (if necessary)
- Have an iPhone and an operable Apple ID, password, and email address and is willing to use these to collect data during the study, acknowledging that data usage, and associated charges, are a result of study participation
- Be willing to complete all study procedures corresponding to their randomization group

Exclusion Criteria

In addition to those who do not meet inclusion criteria, subjects who meet any of the following criteria will be excluded from enrollment:

- Persons who are severely immune compromised
- Persons who are pregnant, as assessed by self-report.

Number of Subjects

Approximately 24 participants are expected to complete Phase 1. The 24 participants from Phase I, plus an additional 20 participants, will complete Phase II for a total of 44 participants.

Pennington Biomedical Research Center employees are not eligible to participate.

Recruitment Methods

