After IRB approval is received, a sample of 44 adults will be recruited from the Baton Rouge, Louisiana area to participate in the study. Phase I will enroll a total of 24 participants. Phase II will enroll an additional 20 participants, totaling 44 enrollees. Recruitment will be completed by PBRC's Recruitment Core. The Recruitment Core manages all community outreach and recruitment services for human research studies at PBRC, such as screening all incoming calls to determine initial study eligibility; assisting in partnership development, specifically with local community groups, physicians, and healthcare facilities; and serving as the first line of contact for all human research study participation. Incoming calls are directed to a call center that is operated by 3 full time recruiters and is equipped with a Uniform Call Distributor (UCD) system. A UCD system expands the capability of a traditional phone system and allows multiple individuals to call simultaneously and be directed to the next available recruiter. The core utilizes an electronic message tracking application that tracks the outgoing phone call activity and a "smart" electronic phone screen system that screens potential participants upon initial phone contact and seamlessly matches them to alternative studies when deemed ineligible for the original study for which they called. In 2012, the core launched a new web-screener for participants to be able to go on-line, choose a study that are interested in and complete a preliminary screening. The system is able to tell the participant upon completion whether they are eligible at that point in the screening process and if they are ineligible the screener will alert them to other studies that they are eligible for and at that point could continue to screen for those studies. If the participant is eligible they are then contacted by a live recruiter to complete the

screening process and schedule their first screening appointment. We anticipate approximately 132 phone screens to enroll 44 participants (3:1 ratio).

Study Timeline

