Phase II of this study is a randomized controlled trial of behavioral nudges via the FoodImage app to reduce household food waste. Phase II will occur in participants' natural environment (free-living conditions) and will include the 24 participants enrolled in Phase I and an additional 20 participants. Phase II, participants will be trained to use the FoodImage app to capture data on food purchases, food waste that occurs during food preparation, food waste that is present after eating, and food waste from food purges in free-living conditions. During data collection, subjects will record the source, reason, and destination of all food waste in the app.

Participants will use the app to collect food waste data for approximately 4 to 7 days over the first week of Phase II and these data serve as baseline data. Participants will then be provided with approximately a one-week break where they will not use the app to track food waste (or do any other study procedures). After the one-week break, participants will return to the center and will be randomly assigned (1:1 ratio) to one of the following groups:

1. Stress Management (Control Group). These participants will use the app to record food waste for approximately 4 to 7 days over the subsequent week. They will also receive information on stress management (Appendix C.1).
2. Food Saver (Intervention Group). These participants also will use the app to record food waste for approximately 4 to 7 days over the subsequent week. They will also be provided with the following:
 - a. Feedback on the amount of food waste their household created during the first week,
 - b. A goal to reduce the next week's food waste by 20% or more, and
 - c. Tips on how to reduce household food waste adapted from current consumer campaigns (e.g., Food: Too Good to Waste Implementation Guide and Toolkit, EPA 2016). This includes advice to limit purchases of unnecessary foods, donate or freeze unwanted and unspoiled foods, prioritize keeping and then eating left-overs, minimize waste during food preparation by preparing and serving smaller portions, purchase only needed foods, and purchase foods that are not near the expiration date (see Appendix C.2). A PBRC staff member will deliver tips to each respondent in this group via in-person and remote sessions (call, text, email, videoconference etc.).

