It is hypothesized that food waste will be equivalent (within 20 grams) when measured with the app vs. direct weights of food waste, while food waste measured with the diary method will not be equivalent to directly weighed food waste. It is also hypothesized that the error from the app will be significantly smaller than error from the diary method.

Phase II analysis objectives include:

- 1) Quantifying baseline distributions for total weight of household food waste

- 2) Determining the effectiveness of the behavioral nudge in altering
 - a) Total daily weight of household food waste,
 - b) Total daily weight of each source of household food waste by occasion, including
 - i) plate waste,
 - ii) food prep waste,
 - iii) purge waste,
 - c) Total daily weight of each source of food waste by food type (e.g., dairy, meat, fruits, etc.) and by macronutrient,
 - d) Daily percent of served food that is wasted, and
 - e) Total amount of food purchased by weight and value.
- 3) Quantifying satisfaction levels with the FoodImage app as measured in Appendix B.1.a. (User Preference Survey) and Appendix B.2.c (User Satisfaction Survey),
- 4) The demographic, household and attitudinal factors measured in Appendix B.2.d (Food Environment Questionnaire) related to
 - a) Effectiveness of the behavioral nudge intervention in reducing food waste generated and all subcomponents listed above, and
 - b) Satisfaction levels with the app as measured in Appendix B.2.c (User Satisfaction Survey).

Withdrawal of Subjects

Subjects may be withdrawn from the study if they are non-compliant with study procedures and they will be notified of their withdrawal via telephone or mail. Subjects may voluntarily withdraw from the study at any time. No additional data will be collected and they will be considered drop outs in the study.

Risks to Subjects

This study involves no greater than minimal risk. The main risk is breach of confidentiality, and the PBRC team will work to minimize this during data collection, handling, and analysis.

Potential Benefits to Subjects

Participants may benefit by increased awareness of their food waste behaviors.

Setting

All research procedures will be conducted at PBRC and in participants' natural environment.

Resources Available

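### The non-compliance withdrawal rule extends past randomisation and ends data collection, so the Phase II comparison can be biased if the rule is used after Visit 2

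*Combined protocol and SAP*

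**What the plan says.** The Withdrawal of Subjects section of the combined protocol and SAP gives staff a discretionary power: "Subjects may be withdrawn from the study if they are non-compliant with study procedures". It then mentions voluntary withdrawal and closes with "No additional data will be collected and they will be considered drop outs in the study". Non-compliance is not defined, no threshold is given, and the rule is not tied to any stage of the study.

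Allocation comes part-way through. Under Phase II (Overview): "After the one-week break, participants will return to the center and will be randomly assigned (1:1 ratio) to one of the following groups". This is Visit 2, at about Day 14. Both arms then record waste in the app for about 4 to 7 days before Visit 3, at about Day 21.

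Number of Subjects makes no allowance for loss: "The 24 participants from Phase I, plus an additional 20 participants, will complete Phase II for a total of 44 participants". Recruitment Methods plans for the same 44.

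The Phase II objectives under Data Analysis and Specimen Management include whether the nudge changes total daily household food waste. They name no analysis set, model or method for missing data.

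**The concern.** Withdrawals before Visit 2 precede allocation and cannot unbalance the arms. Withdrawals after Visit 2 remove people who have already been randomised, during the only week that supplies their follow-up outcome. If the people removed differ in waste from those who stay, and removal is not the same in both arms, the remaining groups are no longer comparable.

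Three features make this plausible here:

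- Compliance and outcome share an instrument. The main task in the follow-up week is logging in the app, and the logged entries are the waste measurement. Whoever logs badly is both a candidate for withdrawal and someone whose measured waste is affected.
- The rule is discretionary and undefined, and no section describes blinding of staff. An interventionist delivers different content to each arm in person and remotely.
- No other section offsets the rule, for example with continued follow-up or analysis by randomised arm.

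At stake is the between-arm estimate of the nudge's effect, which is a stated Phase II objective.

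**Working it through.** The plan states no figure for this issue: Phase II has no power calculation, SD, effect size or dropout rate. There is nothing to reproduce, and the numbers below are illustrations under assumptions.

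**Inputs from the plan.** 44 participants in Phase II (Number of Subjects) allocated 1:1 (Phase II Overview), so 44 / 2 = 22 per arm.

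**Assumed inputs.** The number withdrawn after Visit 2 in each arm; the correlation between non-compliance and waste; a normally distributed outcome in SD units; no true effect; a two-sample t-test at two-sided 5%; and withdrawn participants contributing no outcome at all. The last is the worst case, because the plan does not say that days already recorded are discarded.

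**Step 1, algebra.** If w of 22 are lost from one arm and none from the other:

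bias = −(w / 22) × (mean of withdrawn − mean of retained)

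- w = 2, gap 0.5 to 1.0 SD: 0.05 to 0.09 SD in size.
- w = 3, gap 0.5 to 1.0 SD: 0.07 to 0.14 SD.
- w = 5, gap 0.5 to 1.0 SD: 0.11 to 0.23 SD.

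**Step 2, simulation.** In each simulated trial the w participants with the highest non-compliance score are dropped. The score has the stated correlation with waste.

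| Withdrawn (one arm vs other) | Correlation | Mean shift (SD) | Type I error |
|---|---|---|---|
| 3 vs 0 | 0.5 | −0.12 | about 7% |
| 3 vs 0 | 0.3 | −0.07 | 5.7% |
| 3 vs 0 | 0 | 0 | about 5% |
| 3 vs 1 | 0.5 | −0.07 | 6.1% |
| 2 vs 1 | 0.5 | −0.04 | about 5.6% |
| 1 vs 0 | 0.5 | −0.05 | about 5.5% |
| 3 vs 3 | 0.5 | 0 | about 5.7% |
| 5 vs 0 | 0.5 | −0.19 | about 9% |

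The two steps agree. For 3 vs 0 at correlation 0.5, a shift of 0.12 SD corresponds to a gap of 0.12 × 22 / 3 = 0.88 SD, inside the range used in step 1.

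The negative sign reflects the assumption that non-compliers waste more. If poor loggers record less waste, the sign reverses.

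**Step 3, loss of information.** Apart from bias, the effect detectable with 80% power rises from 0.86 SD at 22 vs 22 to 0.91 SD at 20 vs 20 and 0.96 SD at 18 vs 18.

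**The case against.** The strongest reply is that the harm is conditional several times over. The rule permits withdrawal but does not require it. Only about one week after allocation is exposed. Staff contact, refresher training, extra assistance and payment for completing Phase II all make withdrawal less likely. The trial is a labelled pilot. All of this stands and limits the weight of the point, but none of it sets a rule for what happens if someone is withdrawn after Visit 2.

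A reader might infer more than the text supports in four respects:

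- *That the arms will cease to be the randomised arms.* This follows only if withdrawals occur after Visit 2.
- *That withdrawn participants' data are thrown away.* The plan stops further collection. It does not say that recorded days are deleted or that drop outs leave the analysis. Someone withdrawn late in the week may already have usable days.
- *That Food Saver participants have more procedures to fail.* Feedback is received rather than performed, and the plan nowhere treats missing the 20% goal as non-compliance. Both arms log, attend a session and receive remote contact. Nor does the plan say who decides on withdrawal, so knowledge of the arm is plausible but not stated.
- *That the error rate would reach 14%.* This needs 3 of 22 withdrawn from one arm, none from the other, and exactly the highest wasters removed (a shift of 0.24 SD). Nothing in the plan supports that scenario.

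It can also be argued that the no-further-data sentence concerns voluntary withdrawal only, since it follows that sentence directly. The more natural reading covers both kinds; if only one was meant, the text should say so.

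**Conclusion.** The point holds as a conditional one. As written, the rule allows discretionary removal of randomised participants during the outcome week, on behaviour tied to how the outcome is measured, with no as-randomised analysis to offset it. Bias requires withdrawals after Visit 2 that relate to both arm and waste.

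Under the assumptions shown, the plausible size is modest: about 0.12 SD and a 7% error rate for 3 of 22 lost from one arm at correlation 0.5. With 3 or fewer lost, more balanced or less selective losses give 5% to 6%. Five lost from one arm at correlation 0.5 would give 0.19 SD and about 9%. With no correlation there is no bias. The counts and correlations are assumed, and complete loss of the withdrawn participants' outcome is a worst case. The change is worth making because it is cheap and the rule can be settled before it is used.

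**What to change.** In Withdrawal of Subjects, state that after Visit 2 staff do not withdraw participants from data collection for non-compliance. Follow-up recording and Visit 3 remain on offer unless the participant chooses to withdraw, and all days already recorded are kept. Withdrawal for non-compliance before Visit 2 may stay, since it precedes allocation.

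In the Phase II analysis text, state that participants are analysed in the arm to which they were randomised, and that those with no follow-up days are reported by arm.

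The cost is a few sentences plus one real downside: poorly logged participants stay in and may under-record waste, possibly unequally between arms. To make this visible, report the number of recorded days by arm and add a sensitivity analysis restricted to participants with at least the planned 4 recorded days. That restriction is itself a selection after randomisation, so it should support the as-randomised analysis and not replace it.
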